3.1.5. Full Analysis Set (FAS)

The Full Analysis Set (FAS) will include all enrolled patients who were administered at least one dose of continuous daily of G1T38 (i.e., Cycle 1 Day 1). All analyses using FAS will be conducted by the dose level cohort that was assigned at enrollment. The FAS is the primary analysis set for efficacy analyses, unless otherwise specified.

4. PRIMARY AND SECONDARY ENDPOINTS

For safety endpoints, baseline is defined as the last non-missing value prior to or on the date/time of first administration of investigational medicinal product (IMP) (G1T38 or osimertinib) during the PK period (i.e., Cycle 1 Day -16 for G1T38, or Cycle 1 Day -14 for osimertinib). If the latest pre-dose value is collected on the day of treatment, the time of treatment if available will be used to identify the baseline value. Change from baseline to post-baseline will be calculated as post-baseline value minus the baseline value. Change from baseline is calculated only when both post baseline value and baseline value are non-missing. For efficacy endpoints, the last non-missing value prior to or on the date/time of first administration of daily (i.e., continuous) dosing of the IMP (i.e., Cycle 1 Day 1) will be used as baseline.

4.1 Efficacy Endpoints

4.1.1 General Consideration for Tumor Response Assessment

Progressive disease (PD) and tumor response status will be derived per RECIST v1.1 based on tumor assessment data entered into the EDC by investigators.

The methods used at baseline (i.e., the screening visit) for assessment of tumor burden (computed tomography [CT] or magnetic resonance imaging [MRI] scans of chest and abdomen [including liver and adrenal glands]) must be used at each subsequent follow-up assessment. The baseline assessment shall be performed within 21 days of treatment start. CT or MRI scans obtained prior to informed consent will not need to be repeated if performed within 21 days prior to the first dose of study drug. Subsequent assessments are to be performed every 8 weeks relative to Cycle 1 Day 1 until the date of (i) radiographic disease progression as defined by RECIST 1.1 (Eisenhauer et al, 2009); or (ii) withdrawal of consent to obtain scans; or (iii) receiving subsequent anti-cancer therapy, whichever is earlier. After 18 months of treatment, subsequent tumor assessments shall be performed every 12 weeks (\pm 1 week).

At each tumor assessment visit, an overall visit response by RECIST will be determined programmatically - using the information from investigator's measurement of target lesions (TL), non-target lesions (NTLs) and new lesions collected on electronic case report form (eCRF). The overall response at each time point is also assessed by the investigators and is collected on eCRF.

Antitumor efficacy endpoints include the following based on RECIST v1.1

- Best Overall Response (BOR)
- Objective response rate (ORR) (complete response [CR] or partial response [PR])
- Duration of objective response (DOR), and time to first objective response
- DCR at week 8 (complete response [CR] or partial response [PR] or stable disease [SD])
- PFS

4.1.2 Definitions of Efficacy Endpoints

4.1.2.1 Tumor Responses

Target lesions (TLs)

Measurable disease at baseline is defined as having at least one measurable lesion which is

- ≥ 10 mm in the longest diameter (LD) (except lymph nodes which must have short axis ≥ 15 mm) with CT or MRI; or
- ≥ 10 mm caliper measurement by clinical exam (lesions which cannot be accurately measured with calipers should be recorded as non-measurable); or for lymph nodes which must have short axis ≥ 15 mm by clinical exam; or
- ≥ 20 mm by chest X-ray.

G1 Therapeutics, Inc.
Clinical Study Protocol G1T38-03
Statistical Analysis Plan

In rare cases, lesions measured by methods other than CR, MRI, caliper, or X-ray should be discussed with G1 medical team to determine if the lesions should be counted as measurable disease.

A tumor lesion that has been previously irradiated may be considered measurable if unequivocal growth of the lesion has been demonstrated. A patient can have a maximum of 5 measurable lesions representative of all involved organs (maximum of 2 lesions per organ, both the lymph node and skin will be considered as a single organ) recorded at baseline and these are referred to as target lesions. If more than one baseline scan (prior to or on Cycle 1 Day 1) is recorded, then measurements from the scan that is closest to Cycle 1 Day 1 will be used to define the baseline sum of TLs.

[Table 1](#) gives definition of TL visit responses.

Table 1 Definition of TL visit responses

Visit Responses	Description
Complete Response (CR)	Disappearance of all target lesions. Any pathological lymph nodes selected as target lesions must have reduction in short axis to < 10 mm.
Partial response (PR)	At least a 30% decrease in the sum of diameters of target lesions, taking as reference the baseline sum of diameters as long as criteria for PD are not met.
Progressive disease (PD)	A $\geq 20\%$ increase in the sum of diameters of target lesions and an absolute increase of $\geq 5\text{mm}$, taking as reference the smallest sum on study (i.e. nadir) since treatment started including the baseline sum if that is the smallest on study.
Stable disease (SD)	Neither sufficient shrinkage to qualify for PR nor sufficient increase to qualify for PD, taking as reference the smallest sum of diameters while on study.
Not Evaluable (NE)	Any target lesion measurements are missing and PD status could not be determined based on lesions with non-missing measurements.

Rounding of TL data

For calculation of PD and PR for TLs percentage changes from baseline and previous minimum should be rounded to 1 decimal place before assigning a target lesion response. For example, 19.95% should be rounded to 20.0% but 19.94% should be rounded to 19.9%.

Missing TL data

If any target lesion measurements are missing, then the target lesion visit response is Not Evaluable (NE), unless a convincing argument can be made that the contribution of the individual missing lesions(s) would not change the assigned time point response. The overall visit response will also be NE, unless there is a progression of non-target lesions or new lesions, in which case the response will be PD.

TL too small to measure

If a target lesion becomes too small to measure a value of 5mm will be entered into the database and used in TL calculations, unless the radiologist has indicated and entered a smaller value that can be reliably measured.

Lesions that split

If a TL splits, then the LDs of the split lesions should be summed up and reported as the LD for the lesion that split.

Lesions that merge

If target lesions merge, then the LD of the merged lesion should be recorded for one of the TL sizes and the other TL size should be recorded as 0mm.

Modality change

The same method of assessment (CT or MRI) should be used to characterize tumors at screening and at all follow-up assessments. In case of modality changes, for programmatically derived response, each case should be discussed with medical team to determine if data from substituted approaches should be used, if not, the patient should be considered not evaluable from that point forward. However, a response from the investigator that differs from the programmatically derived response is acceptable if a definitive response assessment can be justified based on the available information.

Non-Target Lesions (NTLs)

All other lesions, including measurable lesions that are not selected as target lesions and all small lesions that do not meet the measurable disease criteria.

The non-target lesion response will be based on the derived timepoint response assessment(s) of NTLs as defined in [Table 2](#):

Table 2 Definition of NTLs visit responses

Visit Responses	Description
CR	Disappearance of all NTLs. All lymph nodes must be < 10 mm short axis.
Non-CR/Non-PD	Persistence of one or more NTLs with no evidence of progression.
PD	Unequivocal progression of existing NTLs. Unequivocal progression is defined as, “an overall substantial worsening in nontarget disease, such that, even in the presence of SD or PR in target lesions, the overall tumor burden has increased sufficiently to merit discontinuation of therapy. A modest “increase” in size of one or more nontarget lesions is usually not sufficient to qualify for unequivocal progression status

G1 Therapeutics, Inc.
 Clinical Study Protocol G1T38-03
 Statistical Analysis Plan

NE	Only relevant when one or some of the NTLs have not been assessed and in the Investigator's opinion they are not able to provide an evaluable overall NTL assessment.
----	---

New lesions

New lesions will be identified via a Yes/No tick box. The absence and presence of new lesions at each visit should be listed alongside the TL and NTL visit responses.

A new lesion indicates progression so the overall visit response will be PD irrespective of the TL and NTL response.

Time Point Response (TPR)

[Table 3-1](#) defines how the previously defined TL and NTL responses will be combined with new lesion information to give an overall response at each time point. The possible overall responses at a visit are CR, PR, SD, PD, and NE.

Table 3-1 Evaluation of Overall Response at Each Time Point – patients with target lesion(s)			
Target Lesions	Non-target Lesions	New Lesions	Overall Response
CR	CR	No	CR
CR	Non-CR/Non-PD	No	PR
CR	Not evaluated	No	PR
PR	Non-PD/not all evaluated	No	PR
SD	Non-PD/not all evaluated	No	SD
NE	Non-PD	No	NE
PD	Any	Yes or No	PD
Any	PD	Yes or No	PD
Any	Any	Yes	PD

CR = complete response, PR= partial response, SD = stable disease, PD = progressive disease,

NE = not evaluable

Source: ([Eisenhauer et al, 2009](#))

For patients without any target lesion, [Table 3-2](#) defines how the previously defined NTL responses will be combined with new lesion information to give an overall response at each time point. The possible overall responses at a visit are CR, Non-CR/Non-PD, PD, and NE.

Table 3-2 Evaluation of Overall Response at Each Time Point – patients without target lesion(s)		
Non-target Lesions	New Lesions	Overall Response
CR	No	CR
Non-CR/Non-PD	No	Non-CR/Non-PD
NE	No	NE
PD	Yes or No	PD
Any	Yes	PD

CR = complete response, PD = progressive disease, NE = not evaluable

Source: ([Eisenhauer et al, 2009](#))

At each tumor assessment visit, an overall time point response of CR, PR, SD, Non-CR/Non-PD, PD or NE by RECIST Version 1.1 will be determined programmatically, using the information from TL, NTLs, and new lesions.

Best Overall Response

Best overall response is defined as the best overall response across all time points. BOR will be determined using overall time point responses up until the last evaluable time point response prior to or on the date of (i) radiographic disease progression as defined by RECIST 1.1 (Eisenhauer et al, 2009); or (ii) withdrawal of consent; or (iii) receiving subsequent anti-cancer therapy, whichever is earlier.

A patient's BOR will be determined based on [Table 4](#). For data-driven scenarios which may not be covered by [Table 4](#), the BOR will be reviewed and determined by the medical advisors and statisticians prior to database lock.

For patients who progress and subsequently have a response, then the best objective response is only derived from assessments up to and including the time of the progression (i.e., it will not include the response after the patient has progressed).

According to tumor assessment schedule (Table 9-1 in protocol), the first post-baseline disease assessment will be obtained at the end of Cycle 2 (study day 56) with a window ± 7 days (study day 49 through day 63). Therefore, a patient will be considered to have BOR of SD or Non-CR/Non-PD if a SD or Non-CR/Non-PD time point response is recorded no earlier than Day 49 since first G1T38 daily continuous dosing (Cycle 1 Day 1).

When the minimum interval (i.e., 4 weeks) for confirmation of CR and PR is not satisfied or if there are no confirmatory scans for CR and PR for a patient, then two ways of assigning BOR will be implemented in the analysis ([Table 4](#)). In the primary analysis, BOR will be assigned as stable disease (SD) according to RECIST 1.1, provided minimum 49 days SD duration criteria met, otherwise BOR will be assigned as PD or NE depends on the response of the confirmation assessment. In the other method, two more response categories will be added as unconfirmed CR and unconfirmed PR.

Table 4 Best Overall Response When Confirmation of CR and PR are Required [a]

First TPR[b]	Subsequent TPR	Best overall response (confirmed CR and PR)	Best Overall Response*(Confirmed and unconfirmed CR and PR)
CR	CR	CR	CR
CR	PR	SD [c] or PD	Unconfirmed CR
CR	SD or Non-CR/Non-PD	SD or Non-CR/Non-PD [c] or PD	Unconfirmed CR
CR	PD	SD or Non-CR/Non-PD [c] or PD	Unconfirmed CR
CR	NE or NA	SD or Non-CR/Non-PD[d] or NE	Unconfirmed CR
PR	CR	PR	Unconfirmed CR
PR	PR	PR	PR
PR	SD	SD	Unconfirmed PR
PR	PD	SD [c] or PD	Unconfirmed PR
PR	NE or NA	SD [d] or NE	Unconfirmed PR
NE	NE	NE	NE

CR = complete response, PR= partial response, SD = stable disease, PD = progressive disease, NE = not evaluable, NA = not available; ORR = Objective Response Rate, TPR = time point response.

- The minimum interval for confirmation of CR and PR is 4 weeks (28 days).
- First appearance of CR or PR per RECIST 1.1.
- Best response will be SD or Non-CR/Non-PD if the first time point overall response is on or after 49 days on study. Otherwise, the best response will be PD.
- Best response will be SD or Non-CR/Non-PD if the first time point overall response is on or after 49 days on study. Otherwise, the best response will be NE.

A best overall response of SD or Non-CR/Non-PD can only be made after the patient has tumor assessment on day 49 (counted from first once-daily dosing date, Cycle 1 Day 1) or later. Otherwise, any tumor assessment indicated stable disease before this time period will have a best response of NE unless PD is identified. If a PD is indicated for the first TPR, then the BOR will be PD regardless of subsequent TPRs.

Subsequent documentation of a CR may provide confirmation of a previously identified CR even with an intervening not evaluable (NE) (e.g., CR NE CR). Subsequent documentation of a PR may provide confirmation of a previously identified PR even with an intervening NE or SD (e.g., PR NE PR or PR SD PR). However, only one (1) intervening NE or SD will be allowed between PRs for confirmation. Note: in the following scenario, PR SD NE PR, the second PR is not a confirmed PR.

Objective Response Rate

Objective response rate will be calculated based on either (1) confirmed tumor responses or (2) confirmed and unconfirmed tumor responses

Objective response will be derived as No/Yes (0/1) variable. For confirmed objective response (OR_{CONFIRMED}), patients with a BOR of confirmed CR or PR will be assigned “Yes”. Patients not having a BOR of confirmed CR or PR will be assigned “No.” Hence, ORR is defined as the proportion of patients with confirmed objective response being “Yes” among the analysis set.

Unconfirmed objective response (OR_{UNCONFIRMED}) will be derived as No/Yes (0/1) variable. Patients with a BOR of confirmed CR, confirmed PR, unconfirmed CR or unconfirmed PR will be assigned “Yes”. All patients with other BOR values will be assigned “No”. Hence, ORR_{UNCONFIRMED} is defined as the proportion of patients with OR_{UNCONFIRMED} being “Yes”.

Disease Control Rate at Week 8

Disease control rate (DCR) at Week 8 is defined as the proportion of patients with a BOR of confirmed CR or confirmed PR or SD or Non-CR/Non-PD at 8 weeks. For patients without measurable lesions at baseline, a BOR of Non-CR/Non-PD will be considered achieving disease control.

Duration of Objective Response

Duration of objective response (DOR) is the time between first objective response of CR or PR and the first date that progressive disease (PD) is objectively documented or death. Patients who experienced an objective response but who do not experience objective PD or death at the time of analysis will be censored at the last adequate assessment date. Adequate assessment is defined as there is sufficient data to evaluate a patient’s disease status. DOR will be calculated only for patients who experience a confirmed objective response.

Time to First Objective Response

Time to first objective response is the time from first dose of once-daily dosing of G1T38 (Cycle 1 Day 1) to first objective response of CR or PR. This variable will be calculated only for patients who experience a confirmed objective response.

Progression-free Survival

Progressive disease (PD) is defined as radiographical determined disease progression based on the criteria by RECIST Version 1.1, which is also referred to as “documented disease progression” in the SAP. PD status is derived from the radiographical assessments by investigators that have been entered to the EDC. A PFS event is defined as a PD event or a death due to any cause.

PFS is defined as the time (months) from start date of continuous daily of G1T38 (i.e. Cycle 1 Day 1) to the date of the first documented PFS event, and the time from start date of continuous daily of G1T38 to the censoring date for those patients that did not experience a PFS event. That is, PFS is calculated as (date of PFS event or censoring – start date of continuous daily of G1T38 + 1)/

G1 Therapeutics, Inc.
Clinical Study Protocol G1T38-03
Statistical Analysis Plan

30.4375. In general the date of PD will be determined using all radiographical assessment data up until the last adequate visit prior to or on the date of (i) disease progression as defined by RECIST Version 1.1, (ii) withdrawal of consent, or (iii) receiving subsequent anti-cancer therapy, whichever is earlier. The “adequate visit” is defined as the visit when all scheduled tumor assessments have been performed. Specifically, if PD and new anti-cancer therapy occurred on the same day for a patient, it is assumed that the PD occurred first.

The primary PFS analysis is to assess PFS before treatment discontinuation. PFS will also be evaluated including tumor assessment data post the last dose of study drug (denoted as the secondary PFS analysis). The censoring rules for the primary PFS analysis are provided in [Table 5-1](#), while the censoring rules for the secondary PFS analysis are presented in [Table 5-2](#).

Table 5-1 PFS Calculation and Censoring Rules for the Primary PFS Analysis

Situation	Date of PD Event or Censored	Outcome
Incomplete or no baseline tumor assessments	Date of Cycle 1 Day 1	Censored
No progression	Date of the last adequate radiological disease assessment with no documented disease progression	Censored
Treatment discontinuation for reasons other than disease progression	Date of the last adequate radiological disease assessment with no documented progression	Censored
New anticancer treatment started prior to documented disease progression	Date of last adequate radiologic assessment no later than the initiation of new anticancer treatment	Censored
Disease progression per RECIST Version 1.1	Date of the first documented progression	PFS event
Death in the absence of documented PD	Date of death	PFS event

Table 5-2 PFS Calculation and Censoring Rules for the Secondary PFS Analysis

Situation	Date of PD Event or Censored	Outcome
Incomplete or no baseline tumor assessments	Date of Cycle 1 Day 1	Censored
No progression	Date of the last adequate radiological disease assessment with no documented disease progression	Censored

G1 Therapeutics, Inc.
Clinical Study Protocol G1T38-03
Statistical Analysis Plan

Treatment discontinuation for reasons other than disease progression, and disease progression documented post last dose of study drug	Date of the last adequate radiological disease assessment	PFS event
Treatment discontinuation for reasons other than disease progression, and no disease progression documented post last dose of study drug	Date of the last adequate radiological disease assessment	Censored
New anticancer treatment started prior to documented disease progression	Date of last adequate radiologic assessment no later than the initiation of new anticancer treatment	Censored
Disease progression per RECIST Version 1.1	Date of the first documented progression	PFS event
Death without a PD	Date of death	PFS event

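### After a rejected imaging-modality change, the SAP makes the derived response not evaluable at every later visit, even when scans return to the baseline modality

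*SAP*

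**What the plan says.** The rule is in SAP 4.1.2.1, under Modality change. The same method should be used from screening onwards. If it changes, the rule for the programmed response has two steps. First, the medical team reviews the case and decides whether the substitute scan counts. Second, where the team rejects it, the SAP continues: "if not, the patient should be considered not evaluable from that point forward". A further sentence then adds that "a response from the investigator that differs from the programmatically derived response is acceptable if a definitive response assessment can be justified" on the available information.

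Other parts of SAP 4.1.2.1 bear on it:

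- **Missing TL data.** A missing target-lesion measurement normally makes that visit NE. Non-target progression or a new lesion still gives PD.
- **Best Overall Response.** "Subsequent documentation of a PR may provide confirmation of a previously identified PR even with an intervening NE or SD", with only one such visit allowed between the two PRs.
- **New lesions.** "A new lesion indicates progression so the overall visit response will be PD irrespective of the TL and NTL response". Table 3-1 agrees.
- **Table 4.** PR followed by NE gives SD if the first response falls on or after day 49, and otherwise NE. On the unconfirmed analysis: "In the other method, two more response categories will be added as unconfirmed CR and unconfirmed PR".
- **Table 5-1.** A patient without progression is censored at the "Date of the last adequate radiological disease assessment with no documented disease progression". "Death in the absence of documented PD" is a PFS event on the date of death.

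**The concern.** The clause makes the patient, rather than the visit or the target lesions, not evaluable. It does not separate a single substituted scan from a lasting switch. A later scan in the baseline modality can be compared with baseline, yet under the literal wording it is still NE.

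That does not fit the SAP's other NE rules. The missing-data rule works visit by visit, and the PR-NE-PR rule presumes that a patient can become evaluable again after an NE.

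At stake are the endpoints built on the derived response: confirmed BOR and ORR, duration of response, time to first response, and PFS. A response that later valid scans would confirm can be reported as SD, and a target-lesion progression on a valid scan can drop out of PFS. The patient stays in the response evaluable set, so the lost response counts as a non-response.

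**Working it through.** The plan gives no figure for this rule, so there is none to reproduce. The check traces one assumed patient through the SAP's own rules.

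**Inputs from the SAP**
- Scans every 8 weeks from Cycle 1 Day 1 (4.1.1).
- At least 28 days to confirm a response; SD only from day 49 (Table 4).
- PFS in months = (event or censoring date − Cycle 1 Day 1 date + 1) / 30.4375 (4.1.2.1, Progression-free Survival).
- At most 36 patients in Part 1, with six in the first cohort (2.3).

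**Assumed record and derived response**

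| Visit | Study day | Scan | Clause as written | NE at affected visit only |
|---|---|---|---|---|
| Week 8 | 57 | CT, PR | PR | PR |
| Week 16 | 113 | MRI, rejected | NE | NE |
| Week 24 | 169 | CT, PR | NE | PR |
| Week 32 | 225 | CT, target-lesion PD | NE | PD |

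**Best response.** As written, Table 4 applies the row for PR followed by NE. Day 57 is past day 49, so BOR is SD and objective response is No. With NE confined to Week 16, the sequence is PR-NE-PR with one intervening NE and a gap of 169 − 57 = 112 days, so the PR is confirmed.

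**Duration of response and time to first response.** Both are calculated only for confirmed responders. As written, the patient drops out of both. With visit-level NE, the patient enters with a first response at Week 8 and progression at Week 32.

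**PFS**
- Visit-level NE: event at 225 / 30.4375 = 7.39 months.
- As written: censored. The date depends on what counts as adequate.
  - Under Duration of Objective Response, adequate means enough data to judge disease status. An NE visit fails this, so censoring falls at Week 8: 57 / 30.4375 = 1.87 months.
  - Under Progression-free Survival, an adequate visit is one at which all scheduled assessments were done, with no mention of NE. Week 24 can then qualify: 169 / 30.4375 = 5.55 months. If Week 32 itself were also accepted as adequate, the time would be 7.39 months, but still as a censoring and not an event.

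**DCR.** SD counts as disease control, so DCR does not change.

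**Size for ORR.** One reclassified responder lowers ORR by 100/n points:

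| n | Drop in ORR (points) |
|---|---|
| 6 | 16.7 |
| 12 | 8.3 |
| 24 | 4.2 |
| 36 | 2.8 |

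With an assumed 18 of 36 responders, ORR moves from 50.0% (Clopper-Pearson 95% CI 32.9 to 67.1) to 17/36 = 47.2% (30.4 to 64.5). The actual denominator is the response evaluable set, which may be smaller than 36, and results are also reported by dose level.

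**The case against.** The strongest reply is that the clause is narrow and well buffered, and much of that stands.

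- It governs only the derived response and follows a case-by-case review. The trigger needs both a departure from the required modality and a refusal by the medical team.
- A justified investigator response may differ from the derived one, and SAP 5.2.9.1 also summarises BOR, ORR and DCR from the investigator's CRF response.
- The planned summary of confirmed and unconfirmed responses keeps the Week 8 PR as an unconfirmed PR.
- A PR confirmed before the modality change is unaffected, and death remains a PFS event.

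These buffers leave a gap. The review has no stated criteria and decides only whether the substituted data are used; after a refusal, the wording makes every later scan NE. The SAP does not say that an investigator response replaces the derived one. SAP 5.2.9.2 and 5.2.9.3 state no analysis of duration of response or PFS from the CRF response. The review of unusual BOR patterns covers only scenarios outside Table 4, and PR followed by NE is inside it.

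A reader might infer that progression by new lesion or non-target disease is lost as well. The documents do not establish this. The new-lesion rule and Table 3-1 give PD whatever the target-lesion response, and the modality paragraph sits among the target-lesion rules. The SAP does not say which rule prevails, so this is an ambiguity. The clear case is target-lesion progression, which is why the worked record uses it.

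A reader might also take 1.9 months as the censoring time. It follows from only one of the SAP's two definitions of adequate.

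**Conclusion.** The point holds for the derived response. After a rejected substitution, the SAP gives no route back to evaluability, which is inconsistent with its own visit-level handling of NE. In the worked record, a confirmed PR becomes SD, the patient leaves the duration-of-response and time-to-response summaries, and a PFS event at 7.4 months becomes a censoring at 1.9 or 5.6 months.

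This rests on a literal reading of the clause, on an assumed patient, and on later scans that truly return to the baseline modality. The documents give no frequency of modality change, so the number of patients affected is unknown and may be zero. Part 1 is descriptive with no formal test (SAP 5.1.1), and Part 2 was not opened (SAP 7). The impact is therefore limited to descriptive estimates, though one patient is visible in a cohort of six. The correction is worth making because it is cheap and removes a conflict that the programmer would otherwise have to settle.

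**What to change.** Replace the clause in SAP 4.1.2.1 (Modality change) with wording such as:

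> If not, the target-lesion response is NE at the affected visit(s) only; scans that return to the baseline modality are evaluated as usual. New lesions and unequivocal NTL progression still give an overall response of PD, except findings attributable to the change in imaging type (Protocol 10.1.1.3).

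The exception is needed because Protocol 10.1.1.3 says that findings caused by a switch between CT and MRI are not new lesions. Without it, the new wording could create false progressions in the very situation it addresses. A lasting switch is still covered, because every visit on the rejected modality is an affected visit.

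Also adopt one definition of an adequate assessment for censoring both PFS and duration of response.

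The cost is a short change to the SAP text and a small edit to the response program before database lock. No new data are needed.
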